### **3 Objectives**

#### **3.1 Primary Objectives**

- 1. To implement an interval bolus SQHC dosing regimen that more closely mimics cortisol, 17OHP and D4A circadian and ultradian rhythms than conventional oral HC dosing.** Up to twelve children (eight analyzable) with CAH, ages 4-18 yrs, will have 24-hr PKPD profiles of cortisol, 17OHP and D4A serum concentrations measured while on oral HC therapy (admission 1), during an initial trial of the SQHC pump (admission 2), and after 6 weeks of SQHC pump treatment (admission 3). An integrated PKPD model will be used to determine cortisol, 17OHP and D4A parameters to compare the duration of time subjects have these concentrations outside their acceptable ranges.

*Hypothesis 1:* Duration of hypocortisolemia and hypercortisolemia will be significantly shorter on SQHC pump therapy (admissions 2 and 3) than with conventional oral HC dosing (admission 1).

*Hypothesis 2:* Duration of time 17OHP and D4A serum concentrations are outside an acceptable range of suppression will be significantly shorter while on the SQHC pump (admissions 2 and 3) than with oral dosing (admission 1).

### **3.2 Secondary/Exploratory Objectives**

1. Physical activity levels: Daily activity and sleep patterns will be assessed by wearing an Actigraph Link accelerometer (Pensacola, FL) for 7 full days (5 weekdays and 2 weekend days) during each study period.
2. Quality of Life and cognitive measures: Quality of life (QoL) measures including NIH toolbox will be measured four times during the study (baseline, and once during each study period). QoL will be measured through the validated PedsQL™ Generic Core Scale and the PedsQL™ Fatigue Scale. *NIH Toolbox Cognitive Tasks*: We will use NIH Toolbox Dimensional Change Card Sort Test (DCCS) from the computer-administered NIH Toolbox to measure children's attention and executive functioning and cognitive flexibility, along with the Flanker Inhibitory Control & Attention Test. A validated sleep and mood survey will also be administered.
3. This proposal will include a utility assessment of a real-time (20 minutes) noninvasive point-of-care salivary testing device [VerOFy® cortisol (VCORT)] in a home setting. While we are not using VCORT to make dosing decisions or diagnoses and formal monitoring will be accomplished using serum cortisol sampling within the protocol, we believe it is important to determine the utility of such a device.
4. An analysis to determine whether PKPD system parameters change with the switch in the route of HC administration from oral to SQHC pump, and after six weeks of SQHC treatment. A preferred pharmacometric analysis for this outcome is to use nonlinear mixed-effects (NLME) regression modeling to estimate PKPD parameters from all data at weeks 1, 7 and 14 simultaneously.

## **4 Study Design**

This is an open-label, non-randomized crossover feasibility trial which will compare oral HC administration with SQHC pump administration in pediatric patients with CAH. Up to twelve children (eight analyzable) with CAH, ages 3-18 years, will have serial cortisol, 17OHP, ACTH and D4A serum concentrations determined over 24 hours while taking conventional oral therapy (Admission 1).

Admission 2 will serve three purposes: a 33-hr SQHC pump evaluation period, patient and parent training with the pump, and a 24-hr PKPD study. During admission 2, we will use each patient's total daily dose (TDD) of HC to determine the doses to be delivered during the 33-hr period. The 24-hr schedule and percentage of the TDD of HC will be as follows: approximately 60% of the TDD of HC will be delivered in 3 equal pulses at 0300, 0600 and 0900. Another 35% will be delivered in 3 equal pulses at 1200, 1500 and 1800 and the remaining 5% at 2100 and 2400. Following delivery of the 9:00 pm, 12:00 am, and 3:00 am pulses, a 24-hr PKPD study will be initiated at the 6:00 am pulse using the same sampling schedule of cortisol, 17OHP, ACTH and D4A as the first admission. After the 24-hr serum sample at 0600 the next morning, the pump will be disconnected and the subject will be sent home on their usual oral HC dosing regimen.

After the SQHC pump therapy PKPD study during admission 2 at week 7, an analysis of the pattern of concentrations will be performed as a safety check. If the cortisol or adrenal steroid concentrations

are generally within acceptable ranges (defined in Aim 1), the same pump settings will be used when initiating the ambulatory pump phase at week 9. If concentrations are outside acceptable ranges, the initial SQHC pump settings will be adjusted from the Admission 2 dosing as needed to attain acceptable concentration ranges. Individual pulse doses may be increased or decreased but the frequency of pulses will be fixed to every 3 hours. After determining appropriate SQHC pump settings, the subjects will return to clinic at week 9 to initiate the 6-week SQHC ambulatory pump therapy phase.

#### 6-WEEK PUMP TREATMENT

All subcutaneous pump settings of hydrocortisone (timing and dose) can only be set by the researchers. The SQ infusion site will be changed every 3 days. As there may be variability in drug absorption associated with different sites of SQ infusion therapy, Each subject will be evaluated for appropriate site for SQ infusion (i.e. gluteal area, abdominal area) to ensure proper placement. A clinician will establish contact every day for the first week via telephone. All patients will be seen at home twice each week during the first and second week at the time of injection site changes and once a week thereafter while on the pump to evaluate proficiency in changing the injection site; to collect blood for cortisol, 17OHP, ACTH, and D4A concentrations; and to inspect the injection site integrity.

*Dose Adjustments During Pump Therapy.* During the 6-week pump treatment, multiple cortisol, D4A, ACTH and 17OHP concentrations will become available and they may suggest, along with clinical impressions, that the pump dosing setting needs to be revised. It is critical to note that subjects will not be required to stay on the initial dosing schedule for 6 weeks. Rather, standard clinical practice will be used to guide SQHC pump dosing adjustments. Specifically, D4A and 17OHP concentrations will be evaluated along with clinical information provided by the patient that are indicative of hypocortisolism such as fatigue, nausea, diaphoresis, low blood pressure, dizziness or headache. This is currently the standard of care for pediatric CAH patients. Should incongruous information be observed, clinical impressions take precedence along with D4A concentrations, and then 17OHP concentration. Cortisol concentrations are not generally part of routine patient care and will play a lesser role in dosing changes. The changes in dose settings may involve increasing or decreasing the HC TDD, or perhaps changing the percentage of TDD administered at a given time, but the 3-hr dosing intervals will remain fixed.

A 24-hr PKPD study will be performed during admission 3 (week 14) using the same sampling schedule as admission 2.

## **5 Subjects**

### **5.1 Study Setting**

There will be three admissions and three outpatient visits held at Nucleus Network (formerly Prism Clinical Research), a 52-bed early phase research site that specializes in complex, phase I and II clinical trials in healthy and numerous patient volunteer populations including pediatrics. It is located within 1 mile from the University of Minnesota campus. Aside from close proximity to the University of Minnesota, Nucleus Network (Prism Research) is located in the epicenter of the Minneapolis/St. Paul Metropolitan area with easy access for all residents to the facility as well as ample free parking for clinical research subjects.

## Interval Bolus Delivery of Cortisol in Children with CAH

Nucleus Network (formerly Prism Clinical Research) has performed studies in pediatric populations and collaborative trials with University of Minnesota Faculty. Nucleus Network (Prism Clinical Research) staff are trained in pediatric phlebotomy. Volunteers and their guardians will be provided a private bedroom with satellite television and wireless internet access that is convenient for both children and their guardians. Nucleus Network (formerly Prism Research) also provides games and movies suitable for all ages.

### **5.2 Eligibility Criteria**

A total of 12 children (6 boys and 6 girls), aged 3-18 years, may be enrolled on this study, to ensure available analysis of 8 completed participants. This study entry is open to children regardless of gender or ethnic background.

#### **5.2.1 Inclusion Criteria**

- Children 3 - 18 years of age.
- Classic CAH as confirmed by hormonal and molecular testing.
- Patients who have been on the same HC dosing regimen for 1 month

#### **5.2.2 Exclusion Criteria**

- Patients with non-classic CAH.
- Patients on:
  - Dexamethasone
  - Prednisone, or
  - inhaled steroids.
- Patients with total daily dose of HC dosing regimen (min 10 mg) that cannot meet the required smallest volume to be delivered by the pump (0.2 mg)
- Non-English speaking patients

#### **Inclusion of Children**

The proposed study will enroll children 3-18 years of age. Justification for the inclusion of children in this study includes: 1) relevance of the disease to the pediatric population; 2) subcutaneous infusion pumps are currently used in the pediatric population to treat diabetes; 3) hydrocortisone succinate, the injectable form of oral hydrocortisone that will be used for hydrocortisone delivery in the subcutaneous infusion pumps, is currently used intramuscularly at home for children with CAH for emergency treatment or when children are sick and unable to take their medicine orally; 4) subcutaneous continuous delivery of hydrocortisone succinate has been used in adults with adrenal insufficiency and in an adolescent with CAH and was well tolerated and safe (Lovas and Husebye, Eur J Endocrinol, 2007; Gagliardi, et al., J Clin Endocrinol Metab, 2014; Oksnes, et al, J Clin Endocrinol Metab, 2014; Bryan, et al., J Clin Endocrinol Metab, 2009); 5) pulsatile delivery of hydrocortisone succinate was performed in normal adults without adverse effects in a study conducted by our collaborator [name] (Russell, et al., Clin Endocrinol, 2014); 6) The Crono P ambulatory subcutaneous infusion pump (CANÈ S.p.A. Medical Technology, Italy) used in [name] study is the only pump specifically designed for preprogrammed (bolus) delivery of glucocorticoids. Inclusion of children in this trial is in accordance with 45 CFR part 46.406—research involving greater than minimal risk and no prospect of direct benefit to individual subjects, but likely to yield generalizable knowledge about the subject's disorder or condition.

#### **Rationale for specific age range**

## Interval Bolus Delivery of Cortisol in Children with CAH

We propose to include children 3-18 years of age because the sequelae of the disease and treatment with steroids such as early epiphyseal closure and short stature, precocious puberty, virilization, adrenal rests, polycystic ovarian disease, and increased risk for osteoporosis and developing metabolic syndrome-related atherosclerotic cardiovascular disease in adult life impact children at an early age and some of them may not be reversible. It is therefore important in this disease to improve treatment early in life to avoid these adverse outcomes.

### **5.3 Recruitment**

Subjects will be recruited from the current CAH patient population at the University of Minnesota Masonic Children's Hospital. The study will be offered to all subjects with CAH at their routine clinical visits.

#### **Resources available**

The multidisciplinary pediatric CAH center at the University of Minnesota, which is the primary referral center for the State and neighboring states, follows over 120 children. Over 50 children have already participated in 6 hour cortisol pharmacokinetic studies (Sarafoglou, et al., J Invest Med, 2015; Sarafoglou, et al., J of Clin Pharma, 2014). 98 children and their families with CAH have participated in an ongoing [name] of Dimes (#6-FY14-440) funded study "Can Molecular Testing Improve Newborn Screening Performance and Outcomes for Congenital Adrenal Hyperplasia?" Overall our experience is that this is a population eager to participate in clinical research because of limitations in current treatments. The PI will delegate much of the screening and recruitment responsibilities to a research nurse and research coordinator. The PI has dedicated research time in her faculty appointment, allowing ample time to provide appropriate oversight and review eligibility of potential participants with study staff.

### **Provisions to Protect the Privacy Interests of Participants**

**Protecting Privacy:** The study consent form will describe in detail any intrusive, uncomfortable, or unfamiliar questions, procedures, or interactions with researchers or study personnel that the participant will be asked to complete. Furthermore, the study consent form will communicate that it is the participant's right to opt-out of any study procedures or the study as a whole or withdraw from the study at any time and this information will be reiterated and revisited periodically throughout the study in advance of intrusive, uncomfortable, or unfamiliar questions procedures or interactions. Participants will not be compelled or pressured to provide information or specimens or study data that they do not wish to provide.

## Interval Bolus Delivery of Cortisol in Children with CAH

**Access to Participants:** Participants have been fully informed of the ways in which their data will/may be used during the informed consent process. The research team has been trained in conducting these conversations and the participants are also assessed for their understanding of consent prior to signing the consent form or initiating any study procedures

### **Consent Process**

Consent forms describing in detail the study procedures, and risks are given to the participant and written documentation of informed consent is required prior to starting intervention/administering study product. Consent will take place at CAH clinic at the University of Minnesota Children's Hospital in a private and confidential room. Participants will have the opportunity to carefully review the written consent form and ask questions prior to signing. The participants will be given the opportunity to take the consent home to discuss with family and caregivers and return on a subsequent day to sign the consent and enroll in the study. Informed consent is a process that is initiated prior to the individual's agreeing to participate in the study and continues throughout the individual's study participation. Extensive discussion of risks and possible benefits of participation will be provided to the participants and their families. Consent forms will be IRB-approved and the participant will be asked to read and review the document. The investigator will explain the research study to the participant and answer any questions that may arise. All participants will receive a verbal explanation in terms suited to their comprehension of the purposes, procedures, and potential risks of the study and of their rights as research participants. Participants will have the opportunity to carefully review the written consent form and ask questions prior to signing. The participants should have the opportunity to discuss the study with others or think about it prior to agreeing to participate. The participant will sign the informed consent document prior to any procedures being done specifically for the study. The participants may withdraw consent at any time throughout the course of the trial. A copy of the informed consent document will be given to the participants for their records. The rights and welfare of the participants will be protected by emphasizing to them that the quality of their medical care will not be adversely affected if they decline to participate in this study.

**Consent Process for Participants Who Are Not Yet Adults (infants, children, teenagers under 18 years of age):** Prior to screening for the study each participant and parent(s)/legal guardian will be informed in detail about the study with its risks and discomforts to be expected. A written parental permission will be obtained from each patient to be involved in the clinical trial by using the IRB-approved Informed Consent Form (ICF) prior to the conduct of any study-related activity. Each participant will be given a copy of the written ICF. The participants will also be instructed that they are free to withdraw their consent and discontinue their participation in the study at any time. The assent from the child or adolescent will be obtained when this is appropriate and when the potential participant is capable of providing assent. The determination of appropriateness and capacity of children in the study to provide assent is made by the PI. For clinical investigations involving greater than minimal risk, permission is generally required from both parents unless only one parent has legal custody, or one parent is deceased, unknown, incompetent, or not reasonably available.

### **Compensation for Research-Related Injury**

In the event that this research activity results in an injury, treatment will be available, including first aid, emergency treatment and follow-up care as needed. Care for such injuries will be billed in the ordinary manner, to the participant or his/her insurance company.

## **6 Study Procedures**

### **6.1 Screening/Baseline**

Once consent has been obtained, the following tests and procedures will be done to determine if the subject is eligible:

- Physical Exam
- Medical History

A subject diary will be provided after consent. This diary will be used by the subject throughout the study to log items such as signs & symptoms, adverse events, medications and dosing.

### **6.2 Treatment period (weeks 1-20)**

#### **6.2.1 Weeks 1-8 (Oral HC)**

##### **6.2.1.1 Week 1**

Once eligibility has been determined, subjects will be admitted into the research unit. Subjects will be admitted for approximately 36 hours. Subjects will have a physical exam and quality of life questionnaire, sleep and mood surveys and NIH toolbox cognitive domain measures administered for baseline values. During Admission 1, the subject's usual doses will be administered at 3 standardized dosing times for the PKPD study: 0600, 1200 and 1800. Changes from usual dosing times are expected to be small and inconsequential for the patient. Immediately prior to the morning dose at 6am, a 3-ml blood sample will be obtained for quantification of cortisol, 17OHP, ACTH and D4A. Samples will then be obtained at 0.5, 1, 1.5, 2, 3, 4, and 6 (noon) hrs after the first dose. The same sampling intervals will be used following the 1200 and 1800 doses, with additional samples collected during the night at 0200, 0400 and 0600. The total blood volume over 36 hrs will be 75 ml, which is well within the acceptable blood volume for this patient population and age range. If a patient is <35 kg, the blood draw will be adjusted based on weight. Also during admission, a 24-hour urine collection will be performed and an aliquot of 20mL will be extracted from two timed 12 hour timed urine collections over the course of 24 hours. Urine samples will be stored under PI supervision for necessary analysis in the future. The IRB will be notified of these analyses when determined. In addition, a total of six saliva samples will be collected at: 0600 (prior to first dose), 0700, 1200 (prior to second dose), 1300, 1800 (prior to third dose) and 1900. Salivary samples will be sent to Quest Diagnostics for adrenal steroid measurements through LC-MS/MS assay. After processing, any remaining saliva samples (during week 1 and the remainder of the study) will be retained by Quest for future research, per subject/family consent. The nurse coordinator will review adverse events, medications and the subject's dairy

##### **6.2.1.2 Weeks 1-6**

Upon discharge, subjects will continue their standard of care oral administration of HC for 6 weeks.

##### **6.2.1.3 Weeks 6**

At the home visit, an Actigraph Link accelerometer will be provided and used to monitor daily activity and sleep patterns for one week. These will be monitored by study personnel. The nurse coordinator will complete their assessment and will review adverse events, medications and the subject's dairy.

#### **6.2.1.4 Week 7 (SQHC Pump 33 hours)**

At week 7, subjects will be re-admitted for Crono P subcutaneous HC (SQHC) infusion pump training in which the device will be used for 33 hrs and include a 24-hr PKPD study while on the SQHC pump. Training will emphasize proper aseptic catheter placement, care of the insertion site, reconstituting the solution and filling the infusion syringe. HC sodium succinate (SOLU-CORTEF) sterile powder will be used for the SQHC pump as it is FDA approved for intramuscular and intravenous routes for CAH and Addison's disease. HC sodium succinate comes in a two-compartment vial (Act-O-Vial) containing a 100 mg dose in the lower compartment and 2 ml sterile water in the upper compartment (100 mg/2 ml). Parents will be instructed to further dilute the solution with another 8 ml of 0.9% normal saline into the infusion syringe, for a final concentration of 100 mg/10 ml (10 mg/ml). Parents will be trained to visually inspect the HC sodium succinate solution for particulate matter and discoloration. The parents of the children seen at the CAH Center are already familiar with the 100 mg Act-O-Vial as the IM HC sodium succinate injection is used at home in cases of acute stress or illness when the children are not able to take oral medication.

Subjects will have a physical exam. Pump therapy during this admission will begin at 9 pm and continue for 33 hours. We will use each patient's total daily dose (TDD) of HC to determine the doses to be delivered during the 33-hr period. The 24-hr schedule and percentage of the TDD of HC will be as follows: approximately 60% of the TDD of HC will be delivered in 3 equal pulses at 0300, 0600 and 0900. Another 35% will be delivered in 3 equal pulses at 1200, 1500 and 1800 and the remaining 5% at 2100 and 2400. Following delivery of the 9:00 pm, 12:00 am, and 3:00 am pulses, a 24-hr PKPD study will be initiated at the 6:00 am pulse using the same sampling schedule of cortisol, 17OHP, ACTH and D4A as the first admission. Urine collection will proceed as the first admission beginning at 0600. Saliva samples will be collected at the same time points as in admission 1 (0600, 0700, 1200, 1300, 1800, and 1900) irrespective of dosing. Salivary samples will be sent to Quest Diagnostics for adrenal steroid measurements through LC-MS/MS assay.

Subjects and families will be given and instructed on how to use an automatic, upper arm blood pressure monitor with a cuff appropriate for the child's size. Subjects will begin monitoring of daily blood pressure upon discharge (see section 9.3 for instructions), to week 13. The staff will review adverse events, medications and the subject's dairy. The Actigraph will be returned at this visit.

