#### **6.2.2 Weeks 9-14 (SQHC Pump)**

### **6.2.2.1 Weeks 9-13**

Week 9 (outpatient visit) The patient will meet [name] and the study nurse coordinator at Nucleus (Prism) for initiating the 6-wk SQHC pump phase. The patient will have a physical exam and the nurse coordinator will review the patient's recorded daily blood pressure, subject diary, adverse events and any medications taken. It is our standard policy to make sure that families have parenteral hydrocortisone to use during emergencies. We will instruct the patients to call [name] before administering any parenteral dose during this phase. After the first four supervised home visits by the nurse coordinator, the family, as instructed will replace the HC infusion syringe and solution, and the site of SQ infusion every 72 hours. As with insulin, we recognize that there may be variability in drug absorption associated with different sites of SQ injection pump infusion therapy. Each subject will be evaluated for appropriate site for SQ infusion (i.e. gluteal area, abdominal area).. Parents will be instructed to visually inspect the parenteral HC solution for particulate matter and discoloration prior to administration into the pump.

After the outpatient visit, during week 9, the subject/family will be called on the days that the RN coordinator is not completing home visits. This call is the review pump use, adverse events and other questions or concerns.

Weeks 9-13: The nurse coordinator will visit subjects at home seven times for safety monitoring, which includes a nursing assessment, and measurement of cortisol, 17OHP, ACTH and D4A concentrations during the SQHC pump period. During the home visits, along with the blood draws, saliva will be collected and measured through VerOFy® cortisol (VCORT) with the remaining salivary sample sent to Quest Diagnostics for free cortisol measurements through LC-MS/MS assay. VCORT is IDE exempt per the requirements outlined in 21CFR812.2(c) and in 21CFR809.10(c). The nurse coordinator will complete their assessment and review the patient's recorded daily blood pressure, subject diary, adverse events and any medications taken. At Visit 13, an Actigraph Link accelerometer will be provided for monitoring daily activity and sleep patterns for one week.

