### **6.2.2.2 Week 14 + 5 days**

At week 14 + 5days, subjects will be admitted for a final SQHC pump 24-hr PKPD study. A physical exam will be performed. This study will occur at the 6:00 am pulse using the same sampling schedule of cortisol, 17OHP, ACTH and D4A as the previous two admissions. Urine collection will proceed as the first admission. Saliva samples will be collected at the same time points as in admission 1 and 2. Salivary samples will be sent to Quest Diagnostics for adrenal steroid measurements through LC-MS/MS assay. QoL, sleep and mood surveys and NIH toolbox cognitive domain measures will be repeated. Once the PKPD study is complete, subject will discontinue use of the pump and resume their usual oral HC regimen. The subject's diary, adverse events and medications taken will be reviewed. The Actigraph will be returned.

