b PKPD: samples to Quest for cortisol (free & total), ACTH plasma, 17-OHP, D4A, & ACTH at all timepoints																			
c Urine collection of 20 mL q12h, store frozen at -80C																			
d Phone call will occur daily during week 9 (except for outpatient & home visit days)																			
e Phone call will occur once a week for weeks 15 through 18																			
f any of the study activities noted below may be performed per investigator discretion																			

Version 10 SEPT 2019

\* Schedule of events will follow as described above with a time window of +/- 1 day for completion of study visits

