## **9.3 Methods to minimize risk**

Subjects will be monitored as per standard of care during treatment with oral cortisol. During the treatment with the SQHC pump, subjects will be monitored inpatient through physical exams for the first 36 hours. Following discharge, for the first four changes in SQ infusion site, a nurse coordinator will travel to the patient's home to evaluate proficiency in changing the injection site; to collect blood for cortisol, 17OHP, ACTH and D4A concentrations; and to inspect the injection site integrity. All patients will be seen at home twice during the first week and second week and once a week thereafter while on the pump. As an additional safety measure for monitoring pump failure that does not trigger an alarm, families will be given and instructed on how to use an automatic, upper arm blood pressure monitor with a cuff appropriate for the child's size. One week prior to the SQHC pump treatment, patients while on oral HC will measure and log child's blood pressure daily in the morning, after 5 minutes rest. When the child is on the pump, families will be instructed to measure and log the child's blood pressure daily. If the mean arterial pressure [MAP =  $[(2 \times \text{diastolic}) + \text{systolic}] / 3$ ] is less than 20 percent of the lowest MAP observed during oral treatment, the blood pressure will be measured 2 more times at 5-minute intervals. Instructions will be provided to the families to notify the PI if 2 of the 3 MAP measurements are below 20 percent of the lowest MAP obtained during oral HC treatment. Parents will be asked to inspect the injection site, tubing, and syringe volume. If no issues are identified and if the blood pressure remains outside the appropriate range after three measures, the parents will be instructed to bring the child to the clinic for clinical evaluation and assessment of pump function. Subjects and their parents will be instructed to contact the Principal Investigator immediately if they develop any signs of symptoms of adrenal insufficiency (e.g. fatigue, nausea, dizziness). The PI can be reached 24 hours a day by her pager number.

The parents of the subjects will be thoroughly trained on the use of the pump, the infusion sets which will be used, and the operational functions of the alarms.

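### Section 6.2.1.4 stops daily home blood pressure at week 13, but section 9.3 requires it for as long as the child is on the pump, which is until admission 3 at week 14 + 5 days is complete

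*Combined protocol and SAP*

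**What the plan says.** Families receive the blood pressure monitor, and are taught to use it, at the week 7 admission. Section 6.2.1.4 sets the period of use: "Subjects will begin monitoring of daily blood pressure upon discharge (see section 9.3 for instructions), to week 13".

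Section 9.3 gives the purpose, "As an additional safety measure for monitoring pump failure that does not trigger an alarm", and the rule for the pump phase: "When the child is on the pump, families will be instructed to measure and log the child's blood pressure daily". It attaches no week number to that rule.

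Section 6.2.2 is headed as the pump phase for weeks 9 to 14. Section 6.2.2.2 fixes its end: "At week 14 + 5days, subjects will be admitted for a final SQHC pump 24-hr PKPD study", and then "Once the PKPD study is complete, subject will discontinue use of the pump and resume their usual oral HC regimen". The footnote to the Schedule of Events allows a window: "Schedule of events will follow as described above with a time window of +/- 1 day for completion of study visits". Under section 7.1.3, pump treatment that has been interrupted is continued after restart until six weeks have been given, so removal can fall later than planned.

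**The concern.** One safeguard has two end points. Under 6.2.1.4 it ends with week 13. Under 9.3 it ends when the pump comes off, which 6.2.2.2 places after week 14 + 5 days. The earlier date sits in the visit description under which the monitor is handed over and the family is trained, so staff could well follow it.

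The check is there to catch a pump that has stopped delivering without an alarm. Section 2 gives hydrocortisone a median half-life of 58 minutes in these children, with most of a dose gone in 4 to 5 hours. An undetected failure could therefore leave a child short of cortisol on the same day. After the first four supervised home visits, families change the syringe and infusion site themselves every 72 hours, and daily telephone contact is limited to the first pump week. A daily home reading is therefore a meaningful part of the cover late in the pump phase.

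**Working it through.** The plan gives no count of monitored days, so there is no figure to reproduce. The check is a day count.

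**Inputs**
- Pump start: week 9 (6.2.2.1)
- Last week of daily readings: week 13 (6.2.1.4)
- Admission 3: week 14 + 5 days (6.2.2.2)
- Visit window: one day either way (Schedule of Events footnote)

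**Convention.** Take week n to start on day 7n.
- Pump start: 7 × 9 = day 63
- Week 13: days 91 to 97
- Admission 3: 7 × 14 + 5 = day 103
- Pump days at home before admission 3: days 63 to 102, which is 103 − 63 = 40

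**Gap if 6.2.1.4 is followed, with week 13 included**
- Days on the pump at home with no daily reading: days 98 to 102 = 5
- Share: 5/40 = 12.5%

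**With the window applied to admission 3**

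| Admission 3 | Home pump days | Days without reading | Share |
|---|---|---|---|
| Day 102 (−1) | 39 | 4 | 10.3% |
| Day 103 | 40 | 5 | 12.5% |
| Day 104 (+1) | 41 | 6 | 14.6% |

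**Other week numbering.** If week n starts on day 7(n − 1) + 1, the pump starts on day 57, week 13 ends on day 91 and admission 3 is day 97. That again gives 97 − 57 = 40 home pump days and a gap of days 92 to 96 = 5.

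**Extension under 7.1.3.** If k days off the pump are made up in full and admission 3 moves by k days, a stop at the end of calendar week 13 leaves 5 + k days uncovered. An end point defined by pump removal leaves none.

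**Why week 13 counts as covered.** Section 6.2.2.1 has the nurse review the daily blood pressure log at the home visits of weeks 9 to 13. The Daily BP row of the Schedule of Events also covers the week 13 column.

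**Which text is the outlier.** In the extracted Schedule of Events, the Daily BP row has 11 consecutive marks from week 7, while weeks 7 to 13 have 10 columns (7, 8, 9, 9 #1, 9 #2, 10 #1, 10 #2, 11, 12, 13). The row therefore seems to run past week 13, in line with 9.3. The table does not align in extraction (18 week labels against 19 visit types), so this is support only, and the finding does not depend on it.

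**The case against.** The best defence is that the protocol already contains the right rule, in the section to which 6.2.1.4 points. Section 9.3 holds the instruction given to families, the blood pressure trigger and the steps to take. It has no calendar end, so it also covers extended pump time. The schedule appears to agree with it. On this view the week 13 limit is a stray phrase, and harm needs staff to prefer it to the governing rule.

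Much of this stands. A site that follows 9.3 has no gap, and nothing suggests that the sponsor meant to stop monitoring early. But the pointer to 9.3 is for instructions. The same sentence states its own stop, and the pointer does not cancel it.

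Two stronger readings are tempting, and the documents do not support either.
- **A gap of 12 days.** A reader might take the limit to mean the start of week 13, which gives days 91 to 102 = 12 of 40 (30%). The log review in 6.2.2.1 and the schedule row both point to readings through week 13, so that figure should not be used.
- **A wrong number of home visits.** Section 6.2.2.1 says "The nurse coordinator will visit subjects at home seven times for safety monitoring" and describes no visit in week 14. But seven is correct for weeks 9 to 13 (2 + 2 + 1 + 1 + 1 = 7), and sections 4 and 9.3 already require a weekly visit while the child is on the pump. The visit is not repeated in one subsection; it is not missing from the plan.

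**Conclusion.** Section 6.2.1.4 is wrong as written: it conflicts with section 9.3 on when a safety check ends. If 6.2.1.4 is followed, about 5 of 40 home pump days (12.5%) lack the daily reading, or 4 to 6 days with the window, and more if the pump phase is extended. If 9.3 is followed, none do.

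The figure assumes that week 13 is included, that the pump starts on the first day of week 9, and that the window moves admission 3 only. Moving the week 9 start would change the denominator but not the number of days missed. The inpatient stay itself is not counted.

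A reader might infer that children would be unmonitored in the last days on the pump. The documents do not support that: symptom instructions, alarm training, weekly nurse visits with bloods and site inspection, and 24-hour access to the investigator all continue. The loss is of one added check, and it depends on which text is followed. No endpoint, sample size, power statement or analysis is touched.

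**What to change.** In section 6.2.1.4, replace the week 13 limit with: *until pump removal at the end of admission 3*. This matches 9.3 and also covers pump time made up under 7.1.3, with no further wording.

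The cost is one phrase in one subsection and about 4 to 6 more days of home readings per child on a monitor already supplied, to which section 9.3 already commits the study.
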